631 Site personnel will call all subjects at 1 week (7 to 13 days) to encourage compliance with treatment

and to confirm that there are no technical problems playing the binocular game for those assigned to

633 binocular treatment. Site personnel will call subjects in the continued spectacle treatment group

634 who switch to binocular treatment at 9 weeks (7 to 13 days after the 8-week visit), again to

635 encourage compliance with treatment and to confirm that there are no technical problems playing

636 the binocular game for those assigned to binocular treatment.

637 **3.5 Follow-up Visit Schedule**

638 The follow-up schedule is timed from randomization as follows:

- 639
 1-week phone call (7 to 13 days from randomization) to inquire about issues with the
 640
 641
 641
 641
 641
- 641 be completed by site personnel)
- 4 weeks ± 1 week (primary outcome)

- 643 8 weeks ± 1 week (secondary outcome)
- Binocular final visit
 - Spectacle group switched to binocular treatment and followed for 8 weeks
- 9-week phone call (Spectacle group only: 7 to 13 days from 8-week exam) to inquire about
 issues with the binocular game (if applicable) and to encourage compliance with treatment
 for all groups (to be completed by site personnel)
- 649
 16 weeks ± 1 week (final visit for group originally randomized to continued spectacle treatment who were switched to binocular treatment)
- 651

652 Additional non-study visits can be performed at the discretion of the investigator.

653 **3.6 Resolution of Amblyopia**

Subjects achieving amblyopic-eye VA equal to or better (0 lines or more lines better) than the better
of the fellow-eye VA at baseline or 4-week visit, will be considered to have resolved and may
discontinue binocular treatment, although these subjects will still return for all remaining follow-up
exams.

658 3.7 Optional Post 8-week Treatment

659 For children originally randomized to binocular treatment, the study ends at 8 weeks.

660

661 Children who were originally assigned to continued spectacle treatment will be offered binocular

treatment for 8 weeks following the 8-week visit. The study will end at the 8-week exam for

663 children who choose not to receive binocular treatment. Children receiving binocular treatment at

the 8 week exam will return at 16 weeks for a follow-up visit. The study will end for these children

at the 16-week visit.

666 **3.8 Follow-up Visit Testing Procedures**

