- 87 If these cases account for $\ge 10\%$ of the data, a sensitivity analysis will be performed in which analyses are
- 88 repeated after substituting missing values for these cases.
- 89
- A logarithm (base 10) transformation will be applied to stereoacuity scores for analyses. Participants
- 91 classified as having nil stereoacuity (worse than 2000 seconds of arc) will be assigned a log score of 3.6
- 92 (the next largest disparity level) to calculate the difference between log converted scores (baseline –
- 93 follow-up).
- 94

98

95 **3.3 Analysis Window**

- 96 The analysis window for visits will be as follows:
- 4-week: 3 to <7 weeks (21 to <49 days) after randomization
 - 8-week: 7 to <15 weeks (49 to <105 days) after randomization
- 99 16-week (visit occurring 8 weeks after initiating binocular treatment for participants initially assigned to spectacles only group): 15 to <23 weeks (105 to <161 days) after randomization
 101

- 102 A visit will be considered missed if it is completed outside of the analysis window or not completed at all.
- 103 Analyses of the amblyopic-eye VA and stereoacuity outcomes will be limited to visits completed within
- 104 the analysis windows.
- 105 106

107 4.0 Analysis Plan for 8-week Randomized Trial Phase

- Analyses outlined in this chapter are limited to data collected at the time of randomization (subsequently 108 referred to as 'baseline') through the 8-week post-randomization follow-up visit. 109
- 110

113

114

111 **4.1 Primary Analysis**

- 112 Two treatment approaches will be evaluated within each of the sub-studies:
 - Binocular treatment: Binocular 'Dig Rush' game played on an iPad device 1 hour per day 5 days per week and spectacle wear (if required)
 - Continued spectacle wear (if required) only •
- 115 116

117 The primary analysis will follow a modified intent-to-treat principle, limited to data from participants who complete the 4-week exam within the pre-specified analysis windows as defined in section 3.3. Data 118 119 from participants with treatment crossover, those who received alternative treatment for ≥ 1 week and participants found to be ineligible after subsequent review of enrollment data will also be included in the 120 primary analysis. There will be no imputation of data for participants who are lost to follow-up or 121 122 withdraw from the study prior to the 4-week exam.

123

124 An analysis of covariance (ANCOVA) adjusting for baseline VA will be performed to compute the 4-

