- The distribution of stereoacuity scores will be tabulated by treatment group at baseline and at each followup visit. Medians and ranges of stereoacuity scores for all visits will be computed by treatment group. Change in ranked stereoacuity scores (≥ 2 levels worse, within 1 level, ≥ 2 levels better) from baseline to
- the 4- and 8-week visits will be tabulated for each group and compared between treatment groups using
- the exact Wilcoxon rank sum test.
- 258

261

4.3 Treatment Compliance, Dose & Game Performance with Binocular Therapy (Binocular Treatment Group)

- In addition to subjective compliance with prescribed treatment based on parent-reported calendars, an
- objective measure of compliance will be obtained from the automated iPad log files for those assigned to
- binocular treatment. The iPad log files record total time playing the game and the contrast level presented
- to the fellow eye. The following sections describe exploratory analyses for compliance measures,
- treatment dose, and game performance in the binocular group. The analyses will be limited to
- 269 participants who completed the follow-up visits within the pre-specified analysis windows (section 3.3).
- 270 No adjustment for multiplicity will be made to these exploratory analyses.
- 271

272 4.3.1 Binocular Treatment Dose, Compliance and Fellow-eye Contrast

- 273 Participants will be prescribed 1 hour per day of binocular game play for 5 days per week as per protocol.
- The cumulative amount of binocular treatment received since baseline (dose) and the percentage of
- prescribed treatment completed (compliance) will be calculated from the log file data for the 4- and 8-
- week visits. Compliance will be calculated as the total amount of binocular treatment received divided by
- the total number of prescribed hours at that time point since baseline. For each follow-up visit, the
- distribution of the cumulative hours of treatment received since baseline (0 to <10, 10 to <20, etc.) and
- the percentage of prescribed treatment completed (0% to 25%, >25% to 50%, >50 to 75%, >75%) will be
- tabulated with computation of descriptive statistics (median and range).
- 281
- 282 The change in contrast level presented to the fellow eye provides a measure of game performance because
- the contrast level in the fellow eye is incremented based on ≥ 15 minutes (or ≥ 30 minutes for participants

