4.3.3 Visual Acuity Change according to Binocular Treatment Dose & Change in Fellow-eye

298 Contrast

The relationship between change in amblyopic-eye VA from baseline to the 4- and 8-week visits with respect to 1) cumulative binocular treatment dose and 2) change in fellow-eye contrast will be examined using scatterplots for evidence of association and form of association. Pairwise correlation between VA change and each of the two factors will be computed using Pearson correlation coefficients if there is evidence of a linear trend based on the scatterplots.

304

305 If there is evidence of a linear relationship between amblyopic-eye VA change from baseline to 4 weeks

306 with either cumulative treatment dose or change in fellow-eye contrast at 4 weeks, a multivariable

regression model that adjusts for baseline VA will be fit to describe this relationship. Collinearity

308 diagnostics will be output from the multivariable regression model to assess whether it is appropriate to

retain both factors in the model. If the two factors are highly collinear, separate regression models will be

310 fit to evaluate the relationship between change in amblyopic-eye VA with each individual factor, adjusted

311 for baseline VA. The analyses described above will also be repeated for the 8-week visit if appropriate.
312

313 Model assumptions for the multivariate regression models will be assessed as described in section 4.1. If

the assumption of linearity between change in amblyopic-eye VA and any of the aforementioned factors

- is not met, then this factor will be categorized into quartiles based on the distribution of the data.
- 316

Given that all participants will be prescribed the same dose of binocular therapy, any differences in

cumulative treatment dose between participants would only be due to treatment compliance, which could

319 be affected by the efficacy of the binocular treatment, differences in motivation to comply with prescribed

treatment and potentially other unmeasured factors. Therefore, results of these analyses will be

- 321 interpreted with caution.
- 322

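### SAP 4.3.3 attributes every dose difference to compliance, but Protocol 3.6 lets resolved children stop the game and stay in the 8-week analysis, which adds a downward component to the exploratory 8-week dose-response

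*SAP*

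**What the plan says.** SAP 4.3.3 relates change in amblyopic-eye acuity at 4 and 8 weeks to cumulative hours of play and to change in fellow-eye contrast. It uses scatterplots, Pearson correlations and, where a linear trend appears, regression adjusted for baseline acuity. SAP 4.3.4 does the same for stereoacuity. Section 4.3.3 then starts from the premise that every child has the same prescription, and concludes that variation in "cumulative treatment dose between participants would only be due to treatment compliance". It concedes that a child's compliance may itself depend on how well the game works, on motivation and on influences that are not measured, and for that reason says that results will be "interpreted with caution"; SAP 4.3.4 repeats the caution.

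SAP 4.3.1 defines percentage compliance as hours received divided by "the total number of prescribed hours at that time point since baseline".

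Protocol 3.6 applies its resolution rule to "Subjects achieving amblyopic-eye VA equal to or better (0 lines or more lines better) than the better" of two fellow-eye readings, one from baseline and one from 4 weeks. Such a child counts as resolved and is allowed to stop the game, but must still attend the remaining exams. Protocol 4.5.1 also leaves continuation to the investigator and parent if diplopia or a new deviation appears. The SAP does not mention resolution.

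**The concern.** The premise that only compliance separates children's doses does not fit the protocol's own rule. A child who resolves at the 4-week visit and stops has fewer 8-week hours because treatment succeeded, not because the family failed to follow the prescription. The child remains in the 8-week analysis with a large gain and a low dose.

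Two outputs are exposed. The 8-week compliance table could record a fully compliant child as a poor complier. The 8-week dose-response acquires a component in which success lowers dose.

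This matters for interpretation, not for the efficacy test. Protocol 1.3 offers poor compliance as a possible reason for the earlier trial's result, and Protocol 5.1 gives possible compliance differences by age as the reason for separate cohorts. Readers will therefore look to these analyses for an explanation. Resolution is also likelier in the younger cohort, so the artefact could distort a comparison of 8-week compliance between cohorts.

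**Working it through.** The documents state no dose-response figure, total of prescribed hours or share resolving, so there is no plan figure to reproduce first.

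**1. Compliance of a child who stops by permission.** The prescription is 5 h per week for 8 weeks (Protocol 3.1), so 40 h by day 56. Hours for a fully compliant child = days × 5/7.

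- Stop on day 28: 28 × 5/7 = 20 h, and 20/40 = 50%, which falls in the SAP's >25% to 50% category.
- Stop on day 21: 15/40 = 37.5%.
- Stop on day 35: 25/40 = 62.5%.
- Stop on day 48: 34.3/40 = 86%.

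These percentages apply if the denominator runs on to the 8-week visit. SAP 4.3.1 does not say whether hours after a permitted stop still count as prescribed.

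**2. The stop is tied to outcome.** Entry requires an interocular difference of at least 3 lines or 15 letters (Protocol 2.2.1). The comparator for resolution is the better of the two fellow-eye measurements, so it is never easier than baseline. Resolution therefore needs a gain of at least 3 lines or 15 letters.

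**3. Share who could resolve.** If every child had only the minimum interocular difference, a normal approximation gives a rough ceiling:

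- Younger, ATS18 (mean 1.09, SD 1.32 lines): z = (3 − 1.09)/1.32 = 1.45, so 7%.
- Younger, Dig Rush pilot mean 1.67 with the observed pooled SD of 1.6: z = (3 − 1.67)/1.6 = 0.83, so 20%.
- Older, ATS18 at 4 weeks (mean 1.8, SD 5.1 letters): z = (15 − 1.8)/5.1 = 2.59, so 0.5%.
- Older, ATS18 at 16 weeks (mean 4.1, SD 6.0 letters): z = (15 − 4.1)/6.0 = 1.82, so 3.5%.

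With assumed spreads of 3–5 or 3–7 lines, about 2% to 10% of the younger cohort resolve. With 15–25 letters, about 1% of the older cohort do.

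**4. Effect on the 8-week slope (simulation, 400,000 children per setting).** Assumed: a true slope of 0.030 lines per hour, and every resolver stopping at the 4-week visit. Earlier-trial compliance is Beta(1, 1.2), with quartiles 21%, 44% and 69% against ATS18's 20%, 46% and 72%. High compliance is Beta(4, 1.5), median about 76%.

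| Interocular difference; 4-week mean/SD (lines) | Resolving | Slope, earlier-trial compliance | Slope, high compliance |
|---|---|---|---|
| 3–7; 1.3/1.2 | 2% | 0.026 | 0.018 |
| 3–5; 1.3/1.2 | 3% | 0.024 | 0.009 |
| 3–7; 1.67/1.6 | 6% | 0.018 | −0.009 |
| 3–5; 1.67/1.6 | 10% | 0.010 | −0.028 |

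Over the same settings, a true slope of zero became −0.003 to −0.056. In the older cohort, a true slope of 0.15 letters per hour became 0.136 (1% resolving) or 0.116 (3%).

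A second simulation, with about 4% to 11% of the younger cohort resolving, expressed the effect as a correlation. A true value of about 0.27 fell to 0.12–0.21 with earlier-trial compliance and to −0.07 to 0.13 with high compliance. Percentage completed, with the denominator ended at the permitted stop, recovered the true value.

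**5. Visit windows (secondary).** The SAP's "4-week: 3 to <7 weeks (21 to <49 days) after randomization" allows 21 × 5/7 = 15.0 h to 48 × 5/7 = 34.3 h for perfect compliers, a ratio of 2.29. At 8 weeks (days 49 to 104), the 8-week prescription caps the range at 35 to 40 h. It reaches 104 × 5/7 = 74.3 h only if play continues to a late visit. With windows alone and no stopping, the simulated slope stayed at 0.030. Adding an assumed time trend of 0.1 line per week, with play continuing to the visit, raised it to 0.0345.

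**The case against.** The strongest reply is that the SAP already concedes the main issue. The sentence goes on to name efficacy as an influence on compliance and asks for caution. These analyses are exploratory and confined to one arm, and the 8-week regression is run only if appropriate. All of that stands. What the caveat lacks is the permitted stop: the SAP neither counts nor separates these children, and the compliance table carries no such caveat.

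A reader might infer more than the documents support:

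- **That the best responders in general are scored as poor compliers.** Only children whose gain reaches their own interocular difference resolve, and stopping is optional.
- **That visit windows add to the downward bias, or more than double the 8-week dose.** Nothing links visit timing to response, and the percentage denominator moves with the visit date. Windows alone gave no downward bias, and the 8-week range is 35 to 40 h under the prescription.
- **That the 8-week dose-response is biased downward overall.** Only this component is known to act downward. Better responders playing more would act upward.
- **That an effective game could be made to look as if it had no dose-response.** The 4-week dose-response is untouched by resolution stops, which follow that visit. Efficacy rests on the randomised comparison.

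**Conclusion.** The concern holds in a limited form. The statement that dose differences are only due to compliance conflicts with Protocol 3.6. As written, the 8-week analyses let success lower dose, directly for acuity and possibly for stereoacuity. The size is small in the older cohort, and small to material in the younger.

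These sizes rest on assumptions that the documents do not supply: the spread of interocular differences, the true slope, the shape of the compliance distribution, the gain between weeks 4 and 8, and every resolver stopping. If fewer stop, the effect shrinks. If compliance is as good as the protocol hopes, it grows. Whether percentage compliance is understated depends on how the undefined denominator is applied. The primary comparison is unaffected, and this point takes no view on whether resolved children should stop.

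**What to change.** 1. Reconcile the sentence in SAP 4.3.3 with Protocol 3.6, and acknowledge the discretionary stops under Protocol 4.5.1.
2. In SAP 4.3.1, end prescribed hours at a permitted stop for resolution, and report how many children stopped for that reason.
3. In the 8-week analyses of SAP 4.3.3 and 4.3.4, use percentage of prescribed treatment completed, with that denominator, as the exposure. Alternatively, relate the outcome to hours up to the 4-week visit for all children. The second option also avoids comparing a 4-week percentage in stoppers with an 8-week percentage in the rest if play tends to fall off over time.
4. Exclude resolved stoppers only as a sensitivity analysis. Exclusion selects on outcome, and in simulation with assumed inputs it left slopes about 6% to 20% below the truth. Substituting 4-week hours for stoppers alone changes nothing, because those are already their cumulative hours.
5. Where raw hours are the 4-week exposure, add visit day as a covariate, because the window allows 15 to 34 prescribed hours.

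The cost is SAP wording and one derived flag, from acuity results, visit dates and iPad logs already collected. The downside is a slightly different exposure definition in an exploratory model.

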4.3.4 Stereoacuity Change according to Binocular Treatment Dose & Change in Fellow-eye Contrast

The relationship between change in stereoacuity from baseline to the 4- and 8-week visits with respect to

1) cumulative binocular treatment dose and 2) change in fellow-eye contrast from baseline will be

examined using scatterplots and Pearson correlation coefficients as described in section 4.3.3. For this

analysis, a logarithm (base 10) transformation will be applied to the raw stereoacuity scores and the

difference between the log converted baseline and follow-up scores will be computed as described insection 3.2.

331

332 If there is evidence of a linear relationship between change in stereoacuity from baseline to 4 weeks with

either cumulative treatment dose or change in fellow-eye contrast at 4 weeks, a multivariable regression

model that adjusts for baseline stereoacuity will be fit to describe this relationship. The same modeling

approach as described in section 4.3.3 will be used. If appropriate the analyses will also be applied to the

8-week visit. As noted in section 4.3.3, results of these analyses will be interpreted with caution.

337

338 4.4 Safety Analyses

- 339 Statistical significance for each formal group comparison of safety outcomes/adverse events was tested at
- a type I error rate of 1% to adjust for multiple testing. Given that spectacle wear and game play on an
- iPad device are not invasive treatments and pose minimal risk, if any, to participants, there are greater
- 342 concerns about the possibility of falsely finding a group difference in safety outcomes/adverse events than
- in missing a difference. Safety analyses will include all participants who completed the follow-up visits
- 344 regardless of the analysis windows.
- 345

346 4.4.1 Visual Acuity in the Fellow Eye

The distribution of change in fellow-eye VA from baseline to 4 weeks will be tabulated. The mean

- change in fellow-eye VA from baseline to 4 weeks will be calculated and compared between treatment
- 349 groups using ANCOVA with adjustment for the baseline fellow-eye VA. The proportion of participants 350 with loss of $\geq 2 \log$ MAR lines (≥ 10 letters) of VA in the fellow-eye from baseline to the 4-week exam
- with 1055 of $\frac{1}{2}$ 2 logMAR lines ($\frac{1}{2}$ 10 letters) of VA in the renow-cyc noni baseline to the 4-week exam 351 will be reported by treatment group and compared using Barnard's exact test. The analyses will be
- 352 repeated for the 8-week visit.
- 353

354 **4.4.2 Ocular Alignment**

The proportion of participants with 1) no baseline heterotropia at distance and/or near who developed a new heterotropia (measured by SPCT) at 4 weeks or 2) a baseline heterotropia at distance and/or near (measured by SPCT) who had an increase of $\geq 10\Delta$ in the pre-existing heterotropia at 4 weeks will be reported by treatment group and compared using Barnard's exact test. The analyses will be repeated for

- 359 the 8-week visit.
- 360

361 **4.4.3** Diplopia

The frequency of diplopia was reported as "Never", "Less than once a week", "Once a week", "Once a day", "Up to 10 times a day", "More than 10 times a day", or "All the time". The distribution of diplopia frequency at baseline, 4 weeks, and 8 weeks will be tabulated by treatment group. Each level of diplopia frequency will be assigned an ordered, numeric score. The change in frequency scores (increased by ≥ 2 levels, within 1 level, decreased by ≥ 2 levels) from baseline to 4 and 8 weeks will be tabulated by treatment group. The frequency scores and the change in scores at 4 and 8 weeks will be compared between treatment groups using the exact Wilcoxon rank sum test. The number of participants with

- 369 monocular diplopia (diplopia that does not go away when the eye is closed or covered) will be reported by
- treatment group, but these cases will not be excluded from the analyses.
- 371
- The above analyses will be performed separately for assessments completed by the participant and by theparent.
- 374

375 4.4.4 Adverse Symptoms

Parents were asked to complete a 5-item symptoms survey regarding the frequency of 1) headaches, 2)

- eyestrain, 3) blurry vision, and if wearing spectacles, how often they 4) look over them or 5) take them
- off. The frequency of each survey item was graded as "Never", "Almost never", "Sometimes", "Often",
- or "Almost Always". For each item, the distribution of symptom frequency at baseline, 4 weeks, and 8
- 380 weeks will be tabulated by treatment group. Each level of symptom frequency will be assigned an
- ordered, numerical score. The change in frequency scores (increased by ≥ 2 levels, within 1 level,
- decreased by ≥ 2 levels) from baseline to 4 and 8 weeks will be tabulated by treatment group. The
- frequency scores and the change in scores at 4 and 8 weeks will be compared between treatment groups

- using the exact Wilcoxon rank sum test. Participants who were not wearing spectacles during the
- randomized trial will not be included in analyses for items regarding spectacle wear.
- 386

